## I. INTRODUCTION

### a) Study Abstract

More than 3 billion people worldwide are at risk of acquiring malaria and HIV-infected pregnant women in Africa are at particular risk. An effective prophylaxis regimen capable of preventing malaria and other common perinatal infections would have great potential to improve adverse birth outcomes. The purpose of this randomized controlled trial is to evaluate a new combination prophylaxis regimen in pregnant women with HIV in Cameroon to determine its efficacy and safety.

### b) Primary Hypothesis

A novel regimen of trimethoprim-sulfamethoxazole (TMPS) in combination with azithromycin (AZ) compared to the standard of care (TMPS) will be more effective in preventing infection with *Plasmodium falciparum* (malaria), *Treponema pallidum* (syphilis), *Chlamydia trachomatis* (CT), *Neisseria gonorrhoeae* (GC), and *Streptococcus agalactiae* (GBS) in HIV-infected pregnant women in Cameroon, Central Africa.

### c) Protocol Summary

We plan a test-of-concept of our central hypothesis by conducting a randomized, placebo-controlled, double-blinded, Phase II trial with the following 3 aims:

Aim 1: Test the efficacy of a combination malaria prophylaxis regimen (TMPS-AZ) compared to the standard of care regimen (TMPS) in reducing malaria in HIV-infected pregnant women. The goal is to determine whether the addition of azithromycin has an impact on the proportion with submicroscopic parasitemia at delivery.

Approach: Pregnant women with HIV will be randomized to the intervention (TMPS-AZ) or to usual care (TMPS) with monthly follow-up visits to receive medications. Blood collected at delivery will be tested by PCR to assess for infection with *Plasmodium falciparum*.

Aim 2: Measure the reduction in prevalence of curable bacterial STIs and GBS colonization after 35 weeks gestation (or at delivery) in the intervention and usual care groups. The goal is to measure the impact of monthly AZ prophylaxis on the prevalence of pathogens that are associated with adverse birth outcomes (*Neisseria gonorrhoeae*, *Chlamydia trachomatis*, *Treponema pallidum*, *Streptococcus agalactiae*).

Approach: Participants will have vaginal and anogenital swabs in late pregnancy or at delivery for GC/CT/GBS nucleic acid amplification testing. Blood will be collected simultaneously for syphilis testing.

Aim 3: Determine the fetal/neonatal safety and adherence/tolerability of TMPS-AZ compared to TMPS. The goal is to collect safety, adherence and tolerability data for this novel regimen used in HIV-infected pregnant women.

Approach: Birth outcomes will be captured by chart review and women will fill out a validated questionnaire to assess medication adherence and tolerance at each visit. The first dose of medication at each visit will be given under directly observed therapy.

## II. BACKGROUND

### **HIV and malaria coinfection in pregnancy is a major public health problem in sub-Saharan Africa.**

Up to 40% of the world's population is at risk of malaria, including 25 million pregnant women in sub-Saharan Africa. The parasite *Plasmodium falciparum* transmitted by the anopheline mosquito causes most serious malaria infections with peak mortality rates in pregnant women and children under 5 years. *P falciparum* is the etiology of 96% of malaria infections in Cameroon with a mean entomological inoculation rate of 3.9 infective bites per person each night.(1-3) HIV, malaria and pregnancy are considered the "triple threat" in terms of maternal morbidity and mortality in Africa.(4) Pregnancy is a risk factor for acquiring malaria, particularly among primigravidae because of parity-dependent development of protective immunity to placental antigens.(5-7) (8) Women with HIV have elevated malaria acquisition risk (RR 1.8), irrespective of parity, and lower rates of malaria specific immunity.(9) Women with HIV also have a 70% increased risk of placental infection and more severe clinical disease than HIV-uninfected pregnant women. (10-13) (14) Studies in pregnancy (including those from our collaborators in Cameroon) among *HIV-uninfected* pregnant women have documented peripheral parasitemia in 22-82% of women.(15-19) Placental malaria is associated with a two-fold increased risk of low birthweight but effective prevention improves maternal severe anemia, low birthweight and perinatal mortality by 27-43%.(6, 20, 21) Malaria also leads to a transient elevation in HIV viral load (7 fold for symptomatic disease) and an increased risk of mother to child HIV transmission which is independent of maternal HIV viral load. (RR 7.9, p=0.025). (11, 22-24)

### **Curable bacterial STIs are common in pregnant women with HIV in Africa and an important cause of maternal and neonatal morbidity.**

Accumulating evidence supports infection as a major cause of spontaneous preterm labor, particularly when it occurs before 30 weeks gestation.(25) The underlying pathogenesis is under study, but proinflammatory cytokines IL-6, TNF, IL-1, metalloproteinase-9 and alterations in the maternal microbiome contribute to uterine activation.(26-30) HIV prevalence in pregnancy is elevated in Africa (10% in urban Cameroon) and antenatal screening suggests a high rate of STIs in women with HIV.(31, 32) In one study, 38% of pregnant women with HIV had CT (compared to 7% in HIV-uninfected), 10% had GC (compared to 3%) and 36% had syphilis (compared to 11%). Up to 90% of pregnant women with early syphilis transmit *Treponema pallidum* to the fetus which can lead to stillbirth, neonatal deaths, congenital syphilis and low birth weight. There are an estimated 200,000 adverse pregnancy outcomes attributable to syphilis in sub-Saharan Africa each year and adequate prevention could reduce stillbirths by 80% worldwide.(33, 34) Although GC/CT infections are generally confined to the lower genital tract, GC acquisition in pregnancy has been associated with preterm birth (aOR 2.1, 95% CI 1.02-3.97) and CT infection with low birthweight (aOR 2.07, 95% CI 1.01-4.24).(35, 36)

**More effective prevention tools for malaria and sexually transmitted infections are needed for the high-risk population of HIV-infected pregnant women.**

Since ART is increasingly available, and HIV-associated mortality rates have fallen, more pregnant women with HIV are in need of malaria prophylaxis.(37) The prevalence of malaria among pregnant women in sub-Saharan Africa ranges from 25-50% despite available prophylaxis.(15-17) The concept of intermittent prophylaxis during pregnancy is to prevent infection and treat asymptomatic infections before negative consequences can occur. Prevention of infection in pregnancy is an attractive concept since antibiotics are only administered during a defined period of exposure and even timely treatment of infection often occurs too late to reverse deleterious inflammatory processes.(38) Although intermittent sulfadoxine-pyrimethamine (SP) is recommended as malaria prophylaxis for many pregnant women, this option is not available for pregnant women with HIV taking TMPS. Co-administration of dual antifolate therapy with TMPS and SP is contraindicated because of side effects including 100-fold higher risk of severe rash. Given this important interaction, in many African countries (including Cameroon), daily TMPS is recommended for malaria prophylaxis in pregnant women with HIV. Available evidence shows that TMPS is as effective as SP (30%-90% efficacy).(39-42) While SP efficacy is jeopardized by emerging resistance, TMPS has good activity against malaria to date.(43, 44)

**Azithromycin (AZ) is a useful agent for co-prophylaxis given its broad coverage, favorable pharmacokinetics, track record of safety in pregnancy and association with improved birth outcomes.**

AZ has anti-inflammatory and immunomodulatory properties and it has been shown to prevent LPS-associated pregnancy loss in a murine model.(45, 46) It concentrates in tissues and has proven efficacy and safety for malaria prevention when used as part of a combination regimen (recommended by WHO to reduce the risk of parasite resistance).(47) AZ has a prolonged half-life (68 hours) and good oral bioavailability (34-52%). Pharmacokinetic studies have shown that increased AZ dosing in pregnancy is not necessary and the AZ dosing schedule with demonstrated efficacy for malaria prophylaxis is 1 gram daily for 3 days.(47-49) One recent study of *HIV-uninfected* women in Papua New Guinea suggested a reduction in low birthweight (RR 0.74, 95% CI 0.6-0.9) and preterm delivery (RR 0.62, 95% CI 0.4-0.9) with the addition of monthly AZ to SP.(50) SP-AZ also significantly improved low birthweight and infant growth parameters at 12 months in Malawi compared to SP alone.(51, 52) For STI prophylaxis, monthly AZ in Kenyan sex workers lowered the incidence of GC by 64% and CT by 62% compared to placebo.(53) AZ 1gm is CDC recommended therapy for CT (97% efficacy).(54, 55) Combination therapy including AZ 1gm is recommended for GC treatment but a single 2 gram dose of AZ has shown 99.2% efficacy.(56) A recent CDC analysis showed 99.6% GC sensitivity to AZ and response rates averaged 96% worldwide.(57, 58) Given more limited exposure to macrolides, GC response rates to AZ are similar or better in Africa.(59) For syphilis treatment, AZ 1-2gm has similar efficacy as benzathine penicillin in certain populations, but AZ resistance has been documented and penicillin remains the treatment of choice.(60) (54) AZ also has activity against other genital tract pathogens which may contribute to birth outcomes (i.e. *Ureaplasma urealyticum* (95%), *Mycoplasma genitalium* (70%)) and *Streptococcus agalactiae* (GBS) (70%).(53, 61, 62) Anogenital GBS colonization during pregnancy is a primary preventable cause of neonatal pneumonia, meningitis and sepsis and HIV-exposed infants are at higher risk of invasive disease.(63) GBS colonization rates range from 20-30% worldwide but antenatal screening is not routine in Africa. (64, 65) We

have an active study to document rates of maternal GBS colonization and capture birth outcomes for exposed infants in Cameroon given the paucity of data. (127)

**Both TMPS and Azithromycin are effective for malaria prophylaxis with favorable safety profiles individually in pregnancy, but additional data on the combination is needed.**

A recent review of malaria prophylaxis regimens in pregnancy discussed the need to capture safety outcomes for new combinations.(66) TMPS is a well-tolerated, inexpensive, widely prescribed, FDA “category C” drug with efficacy against parasitic and bacterial pathogens. It has good pregnancy safety and is part of the WHO-recommended therapy for HIV-infected pregnant women.(67, 68) Azithromycin is a “category B” agent with a favorable safety profile in all trimesters and efficacy against STIs. (48, 69) TMPS/AZ are commonly administered together as prophylaxis in HIV patients and there are no published reports of malaria resistance to TMPS or AZ in Africa.(70)

### III. STUDY OBJECTIVES

As resistance spreads, new options are needed to prevent malaria during pregnancy, particularly among women with HIV-infection. The combination of TMPS and Azithromycin has not yet been studied for efficacy in terms of preventing malaria and other STIs that contribute to adverse birth outcomes.

#### a) Primary Outcomes

**Aim 1** Proportion of women with *Plasmodium falciparum* peripheral parasitemia by microscopy or PCR.

**Aim 2** Prevalence of a composite STI measure (GC, CT, syphilis infections) will be measured in both groups in late pregnancy (>35 weeks gestation) or at delivery and compared between the two groups.

[figure not shown]
**Aim 3** a) Mean infant birthweight; b) Proportion with adverse birth outcomes, including low infant birthweight (<2500 gm), miscarriage (<28 weeks), preterm delivery (<37 weeks), small for gestational age (SGA), stillbirth (>28 weeks), congenital anomaly at birth, early neonatal mortality (within 7 days); and c) maternal adherence to and tolerance of the prophylactic regimen (vomiting, rash/allergic reactions, dizziness, weakness).

#### b) Secondary Outcomes

**Aim 1** a) Episodes of symptomatic malaria during study period; b) geometric mean parasite density at delivery; c) Proportion with placental malaria (impression smear, available on a subset); d) Proportion with anemia at delivery (hgb <11 g/dL); e) Proportion with adverse birth outcomes, including preterm delivery (<37 wks), stillbirth, low birth weight (<2500g) or early neonatal death (<7 days); f) Proportion of infants with poor growth at 6 and 12 months of age.

**Aim 2** a) Proportion with anogenital GBS colonization after 35 weeks GA or at delivery; and b) Maternal puerperal and/or neonatal infections prior to hospital discharge c) Proportion with infection with Mycoplasma genitalium (M gen), Trichomonas vaginalis (T vag), and bacterial vaginosis (BV).

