## VII. STUDY SCHEDULES AND PROCEDURES

	Screen and Enroll	Follow up Visit (1-6)	Sick Visit (1-9)	Term Visit (1)	Delivery Visit (1)	Postpartum (if no Delivery Visit)	Follow Up Call	Infant Follow Up Call or Visit
Timing of Visit/Call	4-28 weeks	Every 4 weeks	As Needed	35-42 weeks	At Delivery	Within 14 days of delivery 	Within 6 weeks	3, 6, 9, 12 months
FORMS 								
Screening Log (Form 1)	X							
Eligibility (Form 2)	X							
Consent and Randomize (Form 3,4)	X							
Baseline Survey (Form 5)	X							
Follow Up Survey (Form 6)		X		X	X	X		
Med Adherence (Form 7)		X	X	X	X	X		
Sick Call Survey (Form 8)			X					
Outcomes and Labs (Form 9)	X	X	X	X	X	X	X	
Adverse Events (Form 10)		X	X	X	X	X	X	X
Postpartum Phone Call (F 11)							X	
Participant Contact Info (Form 12)	X	X	X	X	X	X	X	
Infant Follow Up (Form 13)								X
CLINICAL AND SAMPLING								
Vitals and Exam	X	X	X	X	X	X		
Venipuncture	X		X	X	X	X		
Finger stick	X	X	X	X	X	X		
Vaginal Swab	X			X	X	X		
Placental biopsy					X			
Directly Observed Therapy	X	X	X	X				
LAB TESTING 								
CBC and differential	X			X	X	X		
CD4 Count				X				
HIV Viral Load					X			
Thick smear	X			X	X	X		
RDT		X	X	X				
DBS for PCR	X	X	X	X	X	X		
Syphilis (RPR/TPHA)	X 			X	X	X		
Xpert GC/CT & GBS NAAT				X	X	X		
SUPPLIES PROVIDED								

Bed Net	X							
Condoms	X	X	X	X				
30 day med supply	X	X	X	X				

 Samples collected at postpartum visit only if they were not collected at prior visits

 Lab testing to be performed on site. Additional testing at UAB is not part of this table.

 In cases of fever or clinical suspicion of malaria.

 RPR testing will be performed for women with a positive treponemal test on enrollment if it has not been done.

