## **XI. SAMPLE SIZE CONSIDERATIONS**

AIM 1: To test the hypothesis that the addition of AZ to standard preventive therapy in pregnant women with HIV will be associated with a lower proportion of women with peripheral parasitemia detected by microscopy or PCR at delivery, we assumed a 30% prevalence of parasitemia in the TMPS arm based on prior studies and 15% prevalence in the TMPS/AZ arm. A sample size of 134 pregnant women per arm has 80% power at a two-sided significance level of 0.05 using a chi-square.

We will plan for 15% loss to follow up (LFU) and will recruit 154 women per arm (308 women total).

AIM 2: Based on the sample size of 308 evaluable participants at the time of delivery and an expected prevalence of 30% for one or more STIs (CT 20%, GC 5%, syphilis 5%) there will be >80% power at a two-sided significance level of 0.05 to detect a 50% lower STI prevalence in the intervention arm.

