## **XII. DATA ANALYSIS AND MANAGEMENT**

Data management and analysis will be led by the University of Alabama at Birmingham under the supervision of the study PI ([name]).

The primary analysis will be by intention to treat for women who are randomized and receive at least 1 dose of study medication.

The “per protocol” analysis will be performed on women who came to at least one follow up visit following the enrollment visit, reported excellent (>90%) medication adherence, and had outcomes captured (ie – not lost to follow up).

**Statistical Analysis:** Descriptive statistics will be used to compare the study participants between each arm and the primary analysis will be intention-to-treat for the primary outcome of proportion of women with parasitemia. The analysis plan for categorical outcomes is chi-square, Fisher’s exact tests as needed for small sample sizes and we plan to use t-test and Wilcoxon Rank-Sum tests for continuous outcomes. Women will be considered lost to follow up if they do not have a study visit after 35 weeks or at delivery for outcome ascertainment.

For the secondary outcomes, the significance of differences in proportion will be explored using the Pearson’s  $\chi^2$  test or Fisher’s exact test. Multivariable regression modeling will be used to evaluate baseline factors associated with parasitemia if there is imbalance between the arms despite randomization. Potential covariates include age, parity, educational level, monthly income, marital status, history of negative birth outcomes, CD4 count, ART adherence, bed net usage, malaria treatment received and number of study visits. All analyses will be performed in SAS v 9.3.

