### XIII. STUDY TIMETABLE

	2017	2018	2019	2020
IRB Approval	X			
Hire Study Staff	X			
Training	X			
Enrollment		X	X	
Subject Follow Up		X	X	
Data Processing		X	X	
Data Analysis				X

- a) IRB Approval – see ethical considerations in subsequent section (Section XIV).
- b) Study Staff – One study nurse and one data manager will be hired at each facility and the current CHI-UAB Coordinator will assume the duties of study coordination at both sites. The study PI will be onsite several times a year for 1-2 months at a time during the study period. She will also be on site during training, study initiation and enrollment.
- c) Training – Before the trial begins, study nurses, coordinators, physician co-investigators and laboratory staff will undergo training on study procedures and data collection, including standardized testing methods for malaria and sexually transmitted infections and how to perform a surface examination for congenital anomalies at birth and collect placental biopsies.
- d) Enrollment and Follow Up – In 2014, Mboppi Hospital in Douala had more than 15,000 antenatal care visits and 4000 deliveries. Approximately 400 new pregnant patients are seen each month in clinic and approximately 24 women are HIV-infected (seroprevalence 5.9%). At the Baptist Hospital in Mutengene (BHM), the HIV seroprevalence is 10.2%, and there are 10 new HIV-infected women seen each month in clinic. Approximately 20% of women present for ANC care during their 1st trimester and 75% during the second trimester. Pregnant women routinely have 4 prenatal visits and clinic attendance rates are high with 80% facility delivery rates.

We plan to enroll approximately 18 women each month (12 in Douala, 6 in Mutengene) over an 18 month enrollment period to reach the 308 women needed. This will allow us to have 268 women with evaluable outcomes according to the power calculation stated above (this assumes 15% loss to follow up but we will strive for >95% subject retention).

- e) Data Processing and Analysis – After a three-month period for completion for data entry for the trial, the dataset will be locked and available for analysis. Approximately six months will be required to complete the final report and submit it for publication. Group meetings will be held to determine which manuscripts will be written and the appropriate team members for submitted abstracts and publications.

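### No named method for symptomatic malaria episodes uses time at risk, and the test stated for secondary outcomes would, if applied here, also drop repeat episodes

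*Combined protocol and SAP*

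**What the plan says.** Section III.b lists "Episodes of symptomatic malaria during study period" first among the Aim 1 secondary outcomes. Items c) to f) in the same list are worded as proportions and this one is not. Appendix A also lists it as episodes.

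Section XII has one sentence on testing that is specific to secondary outcomes: "For the secondary outcomes, the significance of differences in proportion will be explored using the" Pearson chi-square or Fisher's exact test. The paragraph before it gives the same tests for categorical outcomes and adds that "we plan to use t-test and Wilcoxon Rank-Sum tests for continuous outcomes". The nearest thing to an exposure term is in the list of possible covariates, "malaria treatment received and number of study visits", but that list belongs to a model for parasitemia and is not an offset.

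The design makes exposure unequal. Appendix A gives entry at 4 to 28 weeks of gestation, and the schedule in section VII places the term visit at 35 to 42 weeks. Section XIII says "Approximately 20% of women present for ANC care during their 1st trimester and 75% during the second trimester". The schedule allows 1 to 6 follow-up visits and up to 9 sick visits per woman.

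**The concern.** A count over unequal time at risk is naturally summarised as a rate. A test on the proportion with any episode ignores how many episodes a woman had and how long she was observed. A rank test on raw counts keeps the first but not the second. Neither gives a rate ratio.

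Partial follow-up adds to this. The primary analysis set in section XII is all randomized women with at least one dose, and 15% loss is planned. Loss is defined by having no visit after 35 weeks or at delivery, so a woman may contribute weeks of observation and then be lost. The plan does not say how she counts for this outcome.

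At stake are the efficiency and interpretability of one secondary comparison. So is the freedom to choose among chi-square, Wilcoxon and t-test after the data are seen.

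**Working it through.** **1. The plan's own figure.** Section XI states that "A sample size of 134 pregnant women per arm has 80% power at a two-sided significance level of 0.05 using a chi-square", for 30% v 15%. With mean proportion 0.225:

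n = [1.96 × √(2 × 0.225 × 0.775) + 0.8416 × √(0.30 × 0.70 + 0.15 × 0.85)]² / 0.15² = 120.5, or 121.

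With continuity correction: (120.5 / 4) × [1 + √(1 + 4 / (120.5 × 0.15))]² = 133.5, or 134.

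The figure reproduces, but it concerns the primary outcome. The documents give no rate, effect size or power for symptomatic episodes.

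**2. Spread of time at risk.** Shortest: 35 − 28 = 7 weeks. Longest: 42 − 4 = 38 weeks. The ratio of the extremes is a little over five.

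**3. Simulation set-up.** From the documents: 154 per arm recruited with 15% loss, 154 × 0.85 = 130.9, so 131 per arm; two-sided 5% level. Assumed:
- Entry for 20% of women at 6 to 14 weeks and for 80% at 14 to 28 weeks, close to the section XIII split.
- Delivery at 39 weeks (SD 2).
- Gamma-Poisson counts with dispersion 0.5.
- True rate ratio 0.6.

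Mean entry is 0.2 × 10 + 0.8 × 21 = 18.8 weeks, so mean follow-up is 39 − 18.8 = 20.2 weeks, or 20.2 / 4.348 = 4.65 months. The central 95% is about 11 to 32 weeks.

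The tests are Pearson chi-square on any episode, Wilcoxon on raw counts, and the log rate ratio per person-time with robust variance.

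**4. Power.** Episodes per control woman = monthly rate × 4.65.

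| Control rate per month | Episodes per control woman | Chi-square | Wilcoxon | Rate model |
|---|---|---|---|---|
| 0.02 | 0.09 | 18% | 18% | 16% |
| 0.03 | 0.14 | 26% | 26% | 25% |
| 0.05 | 0.23 | 34% | 35% | 37% |
| 0.10 | 0.46 | 49% | 54% | 61% |
| 0.20 | 0.93 | 66% | 77% | 86% |

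Type I error was 4% to 5% for all three tests. Repeat runs of this set-up agree within about 3 points, so smaller gaps should not be read as differences.

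**5. Why the yes/no test falls behind.** At mean follow-up, P(any episode) = 1 − (1 + 0.5m)^(−2), where m is the mean count.
- For m = 0.93 v 0.6 × 0.93 = 0.558: 0.534 v 0.389, a risk ratio of 0.73.
- For m = 0.23 v 0.138: 0.196 v 0.125, a risk ratio of 0.64.

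So a rate ratio of 0.6 is diluted more as episodes become commoner.

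**6. Repeats or unequal follow-up?** A second simulation used 134 per arm, rate ratio 0.5, dispersion 1 and a control mean of 0.5 episodes. Chi-square had 67% power with unequal follow-up and 70% with equal follow-up. The rate analysis had 81% and 82%. Most of the gap between the tests therefore comes from repeat episodes, not from unequal time.

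**The case against.** Five points can be made for the plan.

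- **It does not dichotomise the outcome.** A reader might infer that episodes will be reduced to yes/no. The text does not say so. The sentence that "the significance of differences in proportion will be explored" reads most naturally as the method for secondary outcomes that are proportions. It cannot cover all of them, because item b) of the same list is a geometric mean parasite density. Raw counts could go to the Wilcoxon test. This stands, and it narrows the gap to the rate model to about 2, 7 and 9 points at 0.05, 0.1 and 0.2 per month, against 3, 12 and 20 for chi-square. Wilcoxon still ignores person-time and yields no rate ratio.
- **Episodes may be rare.** Both arms receive daily TMPS and bed nets, and parasitemia found at enrollment is treated. At around 0.1 episodes per woman nothing is gained. This stands too: the loss of power is conditional.
- **Randomization balances entry time.** In expectation it does, and the tests hold their level.
- **Bias is not shown.** A reader might infer it from the preterm relative risk of 0.62 in section II. That figure comes from HIV-uninfected women given AZ with SP. The protocol does not state that early delivery or loss is expected to differ by arm. Even if 20% preterm fell to 20 × 0.62 = 12.4%, at an assumed 4 weeks lost each, mean follow-up would change by 0.076 × 4 = 0.3 weeks in 20, or 1.5%. Longer pregnancies on AZ would pull a protective effect toward the null.
- **The stakes are low.** This is one explored secondary outcome in a Phase II test of concept.

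**Conclusion.** The concern holds in limited form. The outcome is a recurrent count over time at risk that differs about five-fold at the extremes, and no named method uses that time. The sentence specific to secondary outcomes would, if applied here, also drop repeats. Whether it applies is left open.

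This is a matter of efficiency and specification, not validity. Under the stated assumptions the shortfall against a rate model runs from nothing at 0.02 to 0.03 episodes per month to about 9 points (Wilcoxon) or 20 points (chi-square) at 0.2. The control rate, rate ratio, dispersion and entry mix are assumptions, and the documents do not show where in that range the trial will fall. Bias would need early delivery or loss to differ by arm. The primary analysis and sample size are untouched. The change is worthwhile because it is cheap, not because a main conclusion depends on it.

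**What to change.** Add to section XII, before unblinding:

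- **Model.** Analyse the number of symptomatic malaria episodes by negative binomial regression (or Poisson with robust variance), with log person-time as offset and terms for arm and site, the stratification factor. Report the rate ratio with 95% CI.
- **Episode.** State which symptoms and which test result make an episode, and the minimum interval before a further positive test counts as new.
- **At-risk window.** State it, for example enrollment to delivery or last contact. The wording in section III.b could be read to run past delivery, since calls continue to 12 months. Women lost early then contribute the time they were observed.
- **Supportive analysis.** Keep the proportion with any episode.

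The cost is a few sentences and a little more analysis work, with no new visits or tests. Section VII.a says forms carry the visit number and date, and Forms 8 and 9 cover sick calls, outcomes and labs. The protocol lists only form titles, so the sponsor should confirm that episode dates and the date of last contact are recorded.
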